### **8.1.3 Safety Follow-up**

A safety follow-up visit will be conducted at Visit 14 (Week 160), which will be 2 weeks after the end of the 2-week taper for participants who are not continuing commercially available GNX (Table 1). This will be the end of study visit for these participants.

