### **2.2.2.1 Ganaxolone Clinical Development Program**

In the US, GNX, under the brand name ZTALMY®, is indicated for the treatment of seizures associated with cyclin-dependent kinase-like 5 (CDKL5) deficiency disorder (CDD) in patients 2 years of age and older. GNX is a Schedule V controlled substance.

Ganaxolone is being further evaluated for use as an ASM in adolescents and adults with status epilepticus (SE) and paediatric and adult patients with seizures associated with tuberous sclerosis complex (TSC).

The completed GNX clinical program comprises Phase 1 studies conducted in healthy participants, adults with migraine, and adults with renal impairment and Phase 2/3 studies were conducted in adults with epilepsy, infants and children with seizure disorders, children with fragile X syndrome (FXS), adults with posttraumatic stress disorder (PTSD), women with postpartum depression (PPD), adults with migraine, adolescents, and adults with SE, and pediatric and adult participants with seizures associated with TSC. In these studies, the efficacy, safety, tolerability, pharmacokinetics (PK), and pharmacodynamics (PD) of GNX were evaluated with an oral dosing duration ranging from 1 day up to more than 5 years, using doses from 50 to 3200 mg/day. Additionally, intravenous (IV) bolus doses ranging from 10 to 30 mg over durations of 2 to 5 minutes, continuous infusion of 10 to 30 mg/hour for 1 hour, or a bolus dose of 6 mg over 5 minutes followed with a continuous infusion of 20 mg per hour for 4 hours were evaluated in healthy participants. In participants with SE, IV infusions of up to 713 mg/day have been evaluated.

As of 10 Oct 2022, an estimated 2172 participants have received at least 1 dose of GNX across the completed studies. This includes 511 participants in Phase 1 and 1661 participants in Phase 2/3 studies. Participants who received GNX ranged in age from 4 months to 88 years.

Formulations used to date in the clinical development program are summarized and listed by study in the Investigator's Brochure (IB).

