#### **4.4 End of Study Definition**

**End of Study (Individual Patient):** A participant is considered to have completed the study if they have completed all study visits up to and including Visit 14 (Week 160) (Table 1).

A participant is considered to have ended their participation when they either complete the study, or when they withdraw and complete the Early Termination visit.

**End of Study (End of Trial):** The end of the study is defined as the date of the last visit of the last participant in the study or last scheduled procedure shown in the Schedule of Activities (SOA; Table 1) for the last participant in the study globally.

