# **7 DISCONTINUATION OF STUDY INTERVENTION AND PARTICIPANT DISCONTINUATION/WITHDRAWAL**

## **7.1 Discontinuation of Study Intervention**

In rare instances, it may be necessary for a participant to permanently discontinue study intervention. If the IP is discontinued at any time, participants should follow the 2-week taper schedule unless otherwise medically indicated such, as drug-induced rash. If the participant discontinues the IP, evaluations listed for the Early Termination Visit (Visit 13 [Week 156]; as shown in the SOA [Table 1]) are to be performed as completely as possible along with the end of study and safety follow-up assessment, as appropriate. Comments (spontaneous or elicited) or complaints made by the participant must be recorded in the source documents. The reason for termination, date of stopping IP, and total amount of IP taken must be recorded in the eCRF and source documents. Discontinuation of IP due to AEs must also be reflected on the AE eCRF page. Participants who discontinue IP should undergo a 2-week or shorter taper period, as clinically indicated. These participants will have a visit 2 weeks after the end of taper to complete the safety follow-up assessments.

The reason for early discontinuation of the IP must be determined by the investigator and recorded in the participant's source documents and on the eCRF. If a participant is withdrawn for more than 1 reason, each reason should be documented in the source document and the most clinically relevant reason should be entered on the eCRF.

Reasons for early termination include but are not limited to the following:

- AE (including pregnancy).
- Protocol violation/protocol deviation.
- Withdrawal by participant or parent(s)/LAR(s).
- Lost to follow-up.
- Lack of efficacy.
- Death.
- Investigator decision.

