### **8.3.3 Electrocardiograms**

12-lead ECGs will be performed to collect the electrical activity of the heart throughout the study to monitor safety. An evaluation of “normal” by a physician must be obtained before the participant is enrolled in the study.

12-lead ECGs will be obtained as outlined in the SOA (see Section 1.3) using an ECG machine that automatically calculates the heart rate and measures PR, QRS, QT, and QTc intervals.

12-lead ECGs will be performed at Visit 1 (First Visit of the OLE), Visit 3 (Week 26), and Visit 14 (Week 160).

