## **5.4. Subject Disposition**

The number of patients screened for this study, the number of rollover (from TSC-2001 and 3001) and the number of patients who received at least one dose of IP will be summarized. The final disposition of all patients who receive IP will be summarized. Reasons for discontinuation of study participation will be summarized. The total number and percentage of patients who complete the study will be summarized.

A listing of patient disposition will be provided. In addition, a summary of the number of patients included in each analysis set will be presented.

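### Participants who taper have no scheduled on-drug ECG after Week 26 of 156, although ECG is a primary endpoint of this long-term safety study

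*Protocol*

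**What the plan says.** Protocol 9.2.2 lists the 12-lead ECG among the primary endpoints, and the primary objective (Protocol 3) is long-term safety and tolerability. Protocol 8.3.3 fixes the schedule: "12-lead ECGs will be performed at Visit 1 (First Visit of the OLE), Visit 3 (Week 26), and Visit 14 (Week 160"). The ECG row of Table 1 agrees. Visit 13, which also serves as the Early Termination (ET) visit, has no ECG.

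Protocol 8.1.3 times Visit 14 "2 weeks after the end of the 2-week taper for participants who are not continuing commercially available GNX". Protocol 7.1 gives the same interval to anyone who stops study drug: "These participants will have a visit 2 weeks after the end of taper to complete the safety follow-up assessments".

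SAP 4.3.4 takes Visit 1 as the ECG baseline and summarises change from it. Participants arrive at Visit 1 already taking ganaxolone. Protocol 5.4 has them continue their parent-study dose, and the Synopsis says that former placebo participants of Study 1042-TSC-3001 are titrated to ganaxolone before that study ends.

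**The concern.** Protocol 8.3.3 presents the ECGs as monitoring that runs through the study, and Amendment 3 lengthened participation from 1 year to about 3. Yet for anyone who tapers, the second and third years contain no scheduled ECG taken on drug. The one late ECG comes after the drug has been withdrawn.

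What is at stake is the interpretation of a primary endpoint. If ganaxolone changed the PR, QRS or QT intervals slowly, or only after prolonged exposure, the Visit 14 value could miss an effect that reverses on withdrawal. If the drug has an early effect already present at Visit 1, its removal would appear at Visit 14 as a change from baseline with the opposite sign. In neither case does the late summary describe ECGs under long-term treatment.

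**Working it through.** **Inputs.** ECGs at Weeks 0, 26 and 160 (Protocol 8.3.3, Table 1). Last treatment visit at Week 156 (Visit 13, Table 1). Taper of 2 weeks, then 2 weeks to follow-up (Protocol 4.1, 8.1.3). Windows of ±14 days on the treatment visits and ±3 days on the safety follow-up (Table 1).

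**1. The plan's own figure.** Visit 14 = 156 + 2 (taper) + 2 (off drug) = Week 160, as stated. The nominal time off drug at the Visit 14 ECG is 14 days, or 11 to 17 days with the ±3-day window.

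**2. Nominal gap.** 156 − 26 = 130 weeks, and 130/156 = 83.3% of the treatment period.

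**3. Gap with both windows.** Visit 3 can fall at Weeks 24 to 28 and Visit 13 at Weeks 154 to 158.
- Shortest: 154 − 28 = 126 weeks.
- Longest: 158 − 24 = 134 weeks.

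**4. Scheduled on-drug time points after Week 26**, for a participant who stays to Week 156 and then tapers:

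| Assessment | Weeks | Count |
|---|---|---|
| Laboratory tests (8.3.4) | 52, 78, 104, 130, 156 | 5 |
| Vital signs (8.3.2) | 52, 78, 104, 130, 156 | 5 |
| 12-lead ECG (8.3.3) | none | 0 |

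Week 26 is therefore the only scheduled post-baseline ECG on drug.

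**5. Early leavers.** Their ET visit follows Visit 13, which has no ECG. Someone who stops at Week 104, for example, has had 104 − 26 = 78 weeks since the last scheduled on-drug ECG.

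**6. What the SAP contrast measures.** Let d be the drug effect on an ECG interval at Visit 1, d + L the effect after long treatment, and T any drift unrelated to drug. Assume that the effect has gone about 2 weeks after the last dose; the documents do not say.
- Visit 14 minus Visit 1 = (0 + T) − d = T − d. L does not appear.
- Visit 13 minus Visit 1 = (d + L + T) − d = L + T. L appears, although d does not.

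If the effect outlasts 2 weeks, Visit 14 retains an unknown part of it, and on-drug and off-drug components are mixed.

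**The case against.** The best case for the schedule is that it is a consistent, deliberate choice. Table 1 and 8.3.3 agree. Protocol 2.2.2.2 and 2.3.1 identify central nervous system effects as the important risk and report no cardiac signal. No rule requires ECGs as often as laboratory tests. Adverse events are collected throughout, and 8.4.5 calls for further investigation of abnormal findings. Participants randomised to ganaxolone in Study 1042-TSC-3001 had a 16-week treatment phase, so their Week 26 ECG reflects about 16 + 26 = 42 weeks of exposure.

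Much of this is fair, and it argues against frequent ECGs. It does not replace a single late on-drug one. Unscheduled ECGs depend on a prompting finding, and an interval change without symptoms gives none. Counting parent-study exposure, 130 of 16 + 156 = 172 weeks (75.6%) remain without a scheduled on-drug ECG.

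Two limits stand. A Visit 13 ECG would still be compared with an on-drug baseline, so it shows change during the extension and not change from before ganaxolone. Moving the ECG also gives up the post-taper reading.

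A reader might also infer that 8.1.3 contradicts 4.4 and removes from the completers those who finish Week 156 and move to commercial ganaxolone. Protocol 8.1.3 says of Visit 14 "This will be the end of study visit for these participants", meaning those not continuing commercial drug. Protocol 4.4 counts as completers those who have "completed all study visits up to and including Visit 14 (Week 160") and ends participation "when they either complete the study, or when they withdraw and complete the Early Termination visit". SAP 5.4 adds: "The total number and percentage of patients who complete the study will be summarized". The documents do not support that stronger reading. The main clause of 8.1.3 schedules Visit 14 without restriction, and the commercial-drug phrase can be read as setting its timing only. Table 1 and 8.3.1, 8.3.2, 8.3.3 and 8.3.5 list Visit 14 with no exemption. The number who would transfer is not given and may be zero, because the only US approval reported is for another disorder: ganaxolone is "indicated for the treatment of seizures associated with cyclin-dependent kinase-like 5 (CDKL5) deficiency disorder (CDD"). The completion percentage is a descriptive row. What remains is unclear wording for this group.

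**Conclusion.** The ECG point holds for participants who taper. None of their scheduled ECGs after Week 26 is on drug: nominally 130 of 156 weeks (83%), or 126 to 134 weeks with windows. The only late change from baseline that SAP 4.3.4 can summarise for them is off-drug against on-drug, which cannot show a long-term on-drug effect.

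The conclusion concerns scheduled ECGs only, and it assumes that the taper and Visit 14 follow the stated timing. The full gap applies to participants who stay to Week 156; for earlier leavers it is shorter. Someone who moved to commercial ganaxolone and did attend Visit 14 could be on drug there and is outside the claim. It would be too strong to say that cardiac safety goes unmonitored: Week 26 is a valid on-drug ECG, and unscheduled ECGs and adverse event reports remain available.

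The change is worth making because it concerns a primary endpoint and is cheap. The commercial-drug wording in 8.1.3 is a minor clarification, with no effect on results that the documents allow one to quantify.

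**What to change.** 1. In Table 1 and 8.3.3, move the late ECG from Visit 14 to Visit 13/ET and state that it is done before down-titration. Table 1 footnote c already puts that visit before the taper, and 7.2 starts the taper at it.
2. Align 8.1.2, which has early leavers taper first and perform the Visit 13 assessments afterwards. Left as it is, it would make their moved ECG an off-drug one again.
3. When reporting, describe the Visit 13 change as change during the extension, since its baseline is on drug.
4. As a wording clarification, state in 8.1.3 whether participants moving to commercial ganaxolone attend Visit 14 and which visit ends the study for them, so that the 4.4 completion definition applies to them without ambiguity. The sponsor should choose; the text does not settle it.

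Moving the ECG adds no procedure, visit or participant, and its price is the post-taper ECG. If that reading is wanted, keep both. This adds one ECG per participant at an existing visit, about 169 at most on the protocol's planned enrolment or 150 on the SAP's. The rest is a few lines of text.

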## 8.2 Efficacy Assessments

Efficacy as determined by a reduction in seizures will be evaluated by collecting daily seizure type, duration, and frequency in a seizure diary. Days in which no seizures occur will also be noted. Changes in seizure intensity/duration, CGI-I, as well as changes in behavior and neuropsychiatric symptoms will be assessed by a variety of clinician and caregiver administered instruments.

Planned timepoints for all efficacy assessments are provided in the SOA (Table 1).

### 8.2.1 Seizure Type and Frequency

The Epilepsy Study Consortium will review participant seizure data and assign the seizure type for each participant in the parent study.

Parent(s)/caregiver(s)/LAR(s) will record daily seizures denoting vernacular name for the seizure type, duration, and frequency in an eDiary.

Seizure types that count towards the efficacy endpoints are defined as the following:

- Focal motor seizures without impairment of consciousness or awareness.
- Focal seizures with impairment of consciousness or awareness with motor features.
- Focal seizures evolving to bilateral, tonic-clonic convulsive seizures.
- Generalized motor seizures including tonic-clonic, bilateral tonic, bilateral clonic, or atonic/drop seizures.

Seizures must have a motor component sufficiently prominent and distinct to clearly establish the observed symptoms as epileptic in origin.

Seizures that **do not count** towards the efficacy endpoints include:

- Focal or generalized nonmotor seizures (eg, absence seizures or focal nonmotor seizures with or without impairment of awareness).
- Infantile or epileptic spasms.
- Myoclonic seizures.

Note: Every seizure reported by the family will be fully described in the study outputs, and each description will include the vernacular name used by the participant or parent(s)/caregiver(s)/LAR(s), as appropriate, to refer to that seizure event as well as the medical seizure type as adjudicated by the Epilepsy Study Consortium. If the parent uses a medically incorrect term to refer to a specific seizure (such as calling a focal seizure with impaired awareness “absence”) it will be permitted as long as they use the term *consistently* for a single seizure type.

Participants or parent(s)/caregiver(s)/LAR(s) are to record administration of the IP and background ASMs in the eDiary during the first year. Compliance with the IP treatment will be assessed by inspecting the participants' eDiary and returned supplies with queries, as necessary.

### **8.2.2 Clinical Global Impression – Improvement**

The CGI-I is a 7-point Likert scale that the parent(s)/caregiver(s)/LAR(s) and clinician uses to rate the change in overall seizure control, behavior, safety, and tolerability after initiation of IP relative to baseline (prior to treatment with IP). The participant will be rated as follows: 1- very much improved, 2- much improved, 3- minimally improved, 4- no change, 5- minimally worse, 6- much worse, and 7- very much worse (Section 10.8).

Clinical Global Impression – Improvement (parent/caregiver/LAR and clinician) will be assessed at Visit 1 (First Visit of the OLE), Visit 3 (Week 26), Visit 5 (Week 52), Visit 7 (Week 78), Visit 9 (Week 104), Visit 11 (Week 130), and Visit 13 (Week 156).

### **8.2.3 Caregiver Global Impression of Change in Seizure Intensity/Duration**

The CGI-CSID is a 7-point Likert scale in which the parent(s)/caregiver(s)/LAR(s) assesses change in seizure intensity and/or duration after initiation of investigational product relative to baseline (prior to treatment with investigational product). The scale ranges from 1- very much improved, 2- much improved, 3- minimally improved, 4- no change, 5- minimally worse, 6- much worse, and 7- very much worse (Section 10.9).

CGI-CSID will be assessed at Visit 1 (First Visit of the OLE), Visit 3 (Week 26), Visit 5 (Week 52), Visit 7 (Week 78), Visit 9 (Week 104), Visit 11 (Week 130), and Visit 13 (Week 156).

### **8.2.4 Short Form 36**

The SF-36 is a multi-purpose survey designed to capture participant or parent(s)/caregiver(s)/LAR(s) perceptions of own health and well-being. The SF-36 has 36 items grouped in 8 dimensions: physical functioning, physical and emotional limitations, social functioning, bodily pain, general, and mental health. Version 2 of SF-36 will be used for this study (Section 10.10).

The SF-36 will be conducted at Visit 1 (First Visit of the OLE), Visit 3 (Week 26), and Visit 5 (Week 52).

## **8.3 Safety Assessments**

Planned timepoints for all safety assessments are provided in the SOA (Section 1.3).

### **8.3.1 Physical/Neurological/Developmental Examinations**

The full physical examination will include the following systems:

- General appearance.
- Head (eyes, ears, nose, and throat).
- Cardiovascular.
- Respiratory.
- Gastrointestinal.
- Genitourinary.
- Musculoskeletal.
- Endocrine/Metabolic.
- Hematologic/lymphatic.
- Skin.
- Other systems as appropriate.

The full neurological examination will include:

- Cranial nerves.
- Motor exam.
- Sensory exam.
- Reflexes.
- Coordination/Cerebellar.

The full developmental examination (applicable only to pediatric participants 1 to 17 years of age, inclusive) will include:

- Speech/language
  - Makes identifiable sounds for specific objects/people.
  - Repeats sounds.
  - Single words.
  - Multiple words.
  - Makes a sentence.
  - Replies to questions using an identifiable sound, single word, multiple word, or sentence.
  - Other abilities.
- Motor
  - Sits with support.
  - Sits independently.
  - Crawls.
  - Stands with support.

- Stands independently.
- Takes steps with assistance.
- Walks independently.
- Other abilities.
- Social
  - Smiles appropriately to situation.
  - Makes eye contact.

The physical/neurological/developmental examinations will be conducted at Visit 1 (First Visit of the OLE), Visit 3 (Week 26), Visit 5 (Week 52), Visit 7 (Week 78), Visit 9 (Week 104), Visit 11 (Week 130), Visit 13 (Week 156), and Visit 14 (Week 160).

### **8.3.2 Vital Signs**

Vital signs including heart rate (HR [bpm]), respiratory rate (RR [breaths/minute]), body temperature measured orally or on the skin, and blood pressure (BP [mmHg]) will be collected at every in-clinic visit.

BP and pulse measurements will be assessed in a sitting position with a completely automated device. Manual techniques will be used only if an automated device is not available.

BP and pulse measurements should be preceded by at least 5 minutes of rest for the participant in a quiet setting without distractions (eg, television, cell phones).

Vital signs will be measured in a sitting position after 5 minutes rest and will include temperature, systolic and diastolic BP, pulse, and RR. Three readings of BP and pulse will be taken. The first reading should be rejected. The second and third readings should be averaged to give the measurement to be recorded.

Vital signs, body temperature, height, and weight will be collected at Visit 1 (First Visit of the OLE), Visit 3 (Week 26), Visit 5 (Week 52), Visit 7 (Week 78), Visit 9 (Week 104), Visit 11 (Week 130), Visit 13 (Week 156), and Visit 14 (Week 160).

### **8.3.3 Electrocardiograms**

12-lead ECGs will be performed to collect the electrical activity of the heart throughout the study to monitor safety. An evaluation of “normal” by a physician must be obtained before the participant is enrolled in the study.

12-lead ECGs will be obtained as outlined in the SOA (see Section 1.3) using an ECG machine that automatically calculates the heart rate and measures PR, QRS, QT, and QTc intervals.

12-lead ECGs will be performed at Visit 1 (First Visit of the OLE), Visit 3 (Week 26), and Visit 14 (Week 160).

### **8.3.4 Clinical Safety Laboratory Tests**

Laboratory safety assessments will be collected to monitor participant safety. Clinical laboratory tests are listed in Section 10.3 and will be collected per the schedule listed in SOA (see Section 1.3). The laboratory reports must be filed with the source documents.

These clinical laboratory assessments will include complete blood count with automated differential, creatinine, blood urea nitrogen, and eGFR calculation (mL/min), comprehensive metabolic panel, as well as serum pregnancy test for all WOCBP. A central laboratory will be utilized by the sites.

The following liver function and eGFR tests will be monitored throughout the study as follows:

- If AST (SGOT) or ALT (SGPT) increases  $> 3$  times ULN during the study, participant should be followed with weekly laboratory repeat testing and continue in study if levels trending down. Participant will be discontinued if levels do not decline to under  $3 \times$  ULN.
- If total bilirubin increases to  $1.5 \times$  ULN or more during study, the participant will be discontinued.
- Participants with significant renal insufficiency, eGFR  $< 30$  mL/min (calculated using the Cockcroft-Gault formula or pediatric glomerular filtration rate [GFR] calculator or Bedside Schwartz), will be discontinued if the criterion is met post baseline.
- If any of the criteria above are deemed clinically significant by the investigator, then the sponsor's medical monitor should be contacted.
- If clinically significant values do not return to normal/baseline within a period of time judged reasonable by the investigator, the etiology should be identified, and the sponsor notified.
- If laboratory values from non-protocol-specified laboratory tests performed at the institution's local laboratory require a change in participant management or are considered clinically significant by the investigator (eg, SAE or Common Terminology Criteria for Adverse Events [CTCAE] Grade 3 laboratory test), then the results must be recorded and discussed with the medical monitor.

Blood samples will be collected for clinical laboratory tests at Visit 1 (First Visit for the OLE), Visit 3 (Week 26), Visit 5 (Week 52), Visit 7 (Week 78), Visit 9 (Week 104), Visit 11 (Week 130), and Visit 13 (Week 156).

The maximum amount of blood collected from each participant over the duration of the study, including any extra assessments that may be required, will not exceed 25 mL. Repeat or unscheduled samples may be taken for safety reasons or for technical issues with the samples, which may increase the total volume drawn. In the pediatric population, the blood volumes collected should be minimized as much as possible.

In addition, urinalysis will be conducted at Visit 1 (First Visit for the OLE), Visit 3 (Week 26), Visit 5 (Week 52), Visit 7 (Week 78), Visit 9 (Week 104), Visit 11 (Week 130), and Visit 13 (Week 156) for all participants.

